**Table 4: Reported Incidences of Secondary Malignancies, CRS, and Neurotoxicity in DLBCL**

Data Source	Description	No. of Patients	Observed Incidence	Incidence Proportion	Clopper Pearson 95% CI	
					lower [for ■ patients]	upper
SEER 18 Regions, 2018	Incidence of non-Hodgkin Lymphoma	25,452	246	0.010	0.004	0.019
	Incidences of secondary malignancies at all sites	25,452	1,950	0.077	0.058	0.097
Abramson, 2020	Incidence of cytokine release syndrome ≥ Grade 3	269	6	0.022	0.013	0.036
	Incidence of neurotoxicity ≥ Grade 3	269	27	0.100	0.079	0.124

DCCPS, Division of Cancer Control and Population Sciences; No., number.

Source: SEER Program (www.seer.cancer.gov) SEER\*Stat Database: Incidence – SEER 18 Regs/National Cancer Institute, DCCPS, Surveillance Research Program, released April 2018, based on the November 2017 submission (Noone, 2018).

## 9.6 Data Management

As this study is based upon secondary use of data, data management activities will be the responsibility of the registry holders.

The databases and software used by the EBMT during the course of the study meet the internationally recognized ethical and scientific quality requirements for designing, conducting, recording and reporting studies involving human subjects. Treatment centers need to be registered to the EBMT Registry system. This registration generates a unique EBMT Center Identification Code (CIC) and includes training on the data collection system. Treatment centers initiate patient reporting through the generation of an EBMT Registry Unique Identification Code, which is unique to every patient. In addition, treatment centers may enter an internal Unique Patient Number (UPN). The Therapy Indication Form will identify that the patient is a recipient of liso-cel and triggers a series of forms appropriate for the specific indication that will be under that unique identification code (UIC).

FormsNet™ 3 (FN3), the CIBMTR’s web-based data collection system, is compliant with the US database security requirements established by the Health Resources and Services Administration Office of Information Technology and with the Food and Drug Administration (FDA) 21 Code of Federal Regulations (CFR) 11. Treatment centers need to be registered as a CIBMTR member and sign a Master Healthcare Data Agreement (MHA) and a Sample Submission Agreement to allow the transfer of data between organizations (CIBMTR and treatment center). Upon MHA completion, treatment center staff are provided access to FN3, and are provided training on the CIBMTR data collection processes including the use of the FN3 system. Treatment centers initiate

patient reporting through the FN3 generation of a CIBMTR Research Identification (CRID) number, which is unique to every patient. The Therapy Indication Form will identify that the patient is a recipient of liso-cel and triggers a series of forms appropriate for the indication. With the CRID, the patient's record can be tracked over time as well as multiple indications. In addition, data are managed through a role-based security model and the CIBMTR data collection, data storage, and data sharing systems are externally audited every year.

At regular intervals (eg, quarterly), the registry holders will provide pseudonymized patient-level data sets to the MAH through a secure file transfer protocol. Data from the 2 registries will be exported following internationally agreed data standards for clinical data sharing (eg, Study Data Tabulation Model [SDTM]-Clinical Data Interchange Standards Consortium [CDISC]) and then combined into Analysis Data Model (ADAM)-like data sets including derived variables to allow consistent and periodic analyses. These data sets will include the characteristics, outcome variables and other covariates. Data dictionaries will be prepared by the registry holders to describe all variables included in the study and their possible values.

## 9.7 Data Analysis

In this noninterventional cohort study, results will be analyzed and reported descriptively; no formal hypothesis testing is intended.

Confidence intervals will be presented as 2-sided 95% intervals unless specified differently for specific analyses.

Summary statistics will consist of the number and percentage of patients in each category for discrete variables, whereas for continuous variables the sample size, mean, median, standard deviation, minimum, and maximum will be given.

All analyses will be carried out for defined subgroups.

A detailed statistical analysis plan (SAP) will be finalized before the first analysis.

### 9.7.1 Analysis Sets

Due to the noninterventional nature of the study, commonly used analysis sets like the intent to treat set or the per protocol set are not defined in this study.

- The **Infused Set (IS)** is defined as all patients selected from the registry and meeting the above-mentioned eligibility criterion, where baseline and disease classification information is available.
- The **Safety and Effectiveness Set (SES)** is defined as all patients from the IS with postinfusion safety or effectiveness information.

### **9.7.2 Analysis of Study Conduct and Study Discontinuation**

An adapted CONSORT diagram will be provided for documenting the number of patients at each reporting schedule. It will also present the patients' situation with regards to their participation in the study and, if relevant, the reason why and when they stopped.

The total number of patients selected from the registries and used within the study, as well as the number and percentage of patients, will also be presented by country and center.

Patient disposition will be summarized and defined as patients who receive liso-cel and are reported to the corresponding registries with either ongoing follow-up, completed follow-up at 15 years or discontinued postinfusion follow-up due to death.

### **9.7.3 Baseline Data: Demographics, Disease History and Prior Therapies**

Treatment centers will be encouraged by the registry holders to register patients into the registry database from 2 weeks prior to the liso-cel infusion to 6 months after infusion. Baseline data are retrospectively reported by data managers after the administration of liso-cel and are collected only once. All information, including any medical history and measurements done prior to the administration of liso-cel, becomes available in the registry as baseline data.

The baseline data will be summarized using descriptive statistics. Individual patient listings will also be provided to support the summary tables. The number and percentage of patients in each of the categories, as listed in [Section 9.3](#) will also be given.

The following baseline data will be presented:

- **Demographics:** Demographic information collected at baseline will be presented using descriptive statistics.
- **Disease History/Status:** Information regarding disease characteristics at diagnosis (eg, lymphoma histology, cytogenetic abnormalities, prognostic information such as IPI score) and status at time of infusion (eg, disease status, ECOG performance score, CNS involvement, comorbidity) will be summarized by frequency counts. The frequency of patients with at least 1 comorbidity, as well as frequency counts of different comorbidities will be presented.
- **Prior Therapy/Prior Medications:** Number of lines of prior therapies will be presented using descriptive statistics. Number of lines of prior therapies in category will be described as frequency counts. A frequency tabulation of the number of patients with the different types of previous therapies (eg, chemotherapy, radiotherapy, surgery) will be given. Also, a frequency tabulation of whether patient had prior hematopoietic cell transplantation (HCT) and the types of prior HCTs will be given.
- **Lymphodepleting Treatment:** A frequency tabulation of the list of lymphodepleting agents will be given.

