## **9.2 Setting**

This noninterventional cohort study will be based on secondary use of data that are collected from existing independent registries, such as, but not limited to, the EBMT and the CIBMTR. Both registries use electronic Registry Case Report Forms (CRFs) onto which data may be entered directly by the treating centers.

All patients included in the EBMT and the CIBMTR registries are treated by their physicians according to real-world clinical practice. Physicians are trained to identify and approach patients treated with at least 1 dose of liso-cel to obtain their written informed consent to transfer their pseudonymized patient-level data to the EBMT or the CIBMTR registries and to be shared with competent health authorities, Marketing Authorization Holder (MAH), and other parties in line with the signed informed consent forms.

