**Table 3: Variables**

Classification	Category	Variable	Description
Baseline (at infusion date)	General Identifiers	Patient Code/ID	Unique de-identified ID for patient
		Reporting Center (RC) Name/ID	Center name or ID reporting to the registry
		Manufacturing Site (MFS) Name/ID	Site name or ID producing the CAR T product
		Apheresis Center (AC) Name/ID	Center name or ID conducting leukapheresis
		Site of Care (SC) Name/ID	Center name or ID treating patient and infusing the CAR T product
Baseline	Product Information and 	Product Name	Name of CAR T product
			
		Product Quality: OOS	Product: out of specification, yes/no
Baseline	Key Treatment Processes and Timing	Patient Registering Date	Date patient was registered into the registry database by the RC
		Leukapheresis Date	Date blood was collected at the AC
		Pre-leukapheresis ALC	ALC count prior to leukapheresis
		Blood Shipment Date	Date blood was shipped from the AC to the MFS
		Blood Arrival Date	Date blood arrived at the MFS
		Manufacturing Start Date	Date MFS started production of CAR T
		Manufacturing End Date	Date MFS completed production of CAR T
		Product Shipment Date	Date CAR T was shipped to the SC
		Product Receipt Date	Date CAR T arrived at the SC
		Lymphodepleting Therapy Date	Date when lymphodepleting therapy started at SC
		Infusion Date	Date when CAR T was infused to the patient at the SC
		Product Infusion Count	Infusion counting number and total number of infusions

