## 9.7.4 Effectiveness Analysis

### 9.7.4.1 Analysis of the Secondary Effectiveness Endpoints

- **Overall response rate (ORR):** ORR is the proportion of patients with a best overall response of complete response (CR) or partial response (PR), where best overall response is defined as the best disease response recorded from liso-cel infusion until disease relapse or progression or start of new anti-cancer therapy, whichever happens first. If best response is collected by both computerized tomography (CT) and positron emission tomography (PET) methods, best response per PET overrules best response per CT.
- **Complete response rate (CRR):** CRR is the proportion of patients with a best overall response of CR, where best overall response is defined as the best disease response recorded from liso-cel infusion until disease relapse or progression or start of new anti-cancer therapy, whichever happens first. If best response is collected by both CT and PET methods, best response per PET overrules best response per CT.
- **Duration of response (DoR):** DoR is defined as the time from the date of first documented disease response (CR or PR) to the date of first documented progression or first documented relapse, or to date of death due to primary disease, whichever happens first. Patients who are alive and didn't experience disease progression, relapse or death due to primary disease before last contact date will be censored at that time, but no censoring will be done for additional treatment.
- **Progression-free survival (PFS):** PFS is defined as the time from the date of first liso-cel infusion to the date of event defined as the first documented relapse or progression or death due to any cause, whatever happens first. Patients who did not reach such events before the last contact date will be censored at that time, but no censoring will be done for additional treatment.
- **Overall survival (OS):** OS is defined as the time from the date of first infusion to the date of death due to any cause. All patients will be followed for survival information, regardless of whether they receive additional treatment postinfusion. Patients who are alive at last contact date will be censored at that time, but no censoring will be done for additional treatment. OS will be calculated according to the formula:  
$$\text{OS (months)} = (\text{date of death or censoring} - \text{infusion date} + 1) / 30.4375.$$

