- **Time to next treatment (TTNT):** TTNT is defined as the time from the date of liso-cel infusion to next treatment of the primary disease (excluding consolidation and maintenance therapies). Patients who did not receive any new treatment for the primary disease before the last contact date or before death will be censored at the last contact date or death date. TTNT will be calculated according to the formula:  
$$\text{TTNT (days)} = \text{date of start of the next therapy line or censoring} - \text{infusion date} + 1$$
- **Time-to-Event (TTE) Analysis:** For DoR, PFS, OS, and TTNT, Kaplan-Meier (KM) estimates and the associated 95% CIs of the median, 25th and 75th percentile will be presented. The 2-sided 95% CIs will be computed using the log-log transformation. The survivor function will be displayed graphically using a KM curve.

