### **10.3 Informed Consent**

Data will only be part of the PASS if the patients (and parental/legal representative, when applicable) have given their voluntary informed consent to allow data to be provided to the EBMT or the CIBMTR and to be shared with competent health authorities, MAH, and other parties in line with the signed informed consent forms.

The ICF used to consent patients will be based upon the ICF templates of the EBMT and/or the CIBMTR, updated in line with the treatment center's standard practices/regulations to fulfill data protection and/or national requirements for informed consent, and allowing the registry holders to share pseudonymized patient-level data with third parties, including competent health authorities and the MAH, if the patient agrees. The registry holders will obtain the necessary approvals from Ethics Committees, Independent Review Committees, Regulatory Authorities, and/or other local governance bodies for conducting their registry and implementing their ICF within the participating treatment centers.

In case a patient treated with liso-cel in the postmarketing setting develops a secondary malignancy of suspected T cell origin, a separate ICF will be used for tumor tissue sample collection and liso-cel transgene testing outside the scope of this PASS.

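### Consent is sought after treatment and registration may come up to 6 months after infusion, yet OS, PFS and TTNT run from infusion without delayed entry, so early deaths may be selectively missing

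*Protocol*

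**What the plan says.** Four parts of the protocol bear on this.

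- **Consent.** Section 9.2: "Physicians are trained to identify and approach patients treated with at least 1 dose of liso-cel to obtain their written informed consent". Section 10.3: "Data will only be part of the PASS if the patients (and parental/legal representative, when applicable) have given their voluntary informed consent".
- **Registration window.** Section 9.7.3 encourages centers to "register patients into the registry database from 2 weeks prior to the liso-cel infusion to 6 months after infusion". Baseline data are entered retrospectively.
- **Time origin and estimator.** Section 9.7.4.1: "OS is defined as the time from the date of first infusion to the date of death due to any cause" and "PFS is defined as the time from the date of first liso-cel infusion to the date of event". TTNT also starts at infusion. The estimator is given as follows: "For DoR, PFS, OS, and TTNT, Kaplan-Meier (KM) estimates and the associated 95% CIs of the median, 25th and 75th percentile will be presented". No entry time is mentioned.
- **Dates available.** Table 3 lists both the infusion date and the Patient Registering Date, described as "Date patient was registered into the registry database by the RC". No consent date appears among the variables shown.

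Both analysis sets in section 9.7.1 start from patients selected from the registry, so an infused patient who is never registered is in neither. Section 9.9 concedes incomplete consent, attrition and possibly poor capture of mortality, and plans to reconcile shipped product with each center's reporting. It does not mention death or incapacity before consent or registration. The ENCePP checklist (item 7.3, whose examples include time-related bias) is ticked as addressed in section 9.9.

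**The concern.** If a patient has to be alive and able to consent in order to be entered, someone registered in month 5 could not have contributed a death in months 0 to 5. Counting that patient as at risk from day 0 is left truncation handled as if it were complete follow-up from infusion. The early part of the OS and PFS curves is then too high, and more patients do not cure it. For TTNT the direction is less certain, because death is a censoring event there.

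The primary safety endpoints are exposed in a narrower way. Section 7.2.2 places neurologic symptoms within about 4 weeks of infusion, well inside the registration window. A toxicity that kills or incapacitates a patient before consent could keep both the patient and the event out of the data.

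**Working it through.** The protocol states no figure for this bias, so there is nothing to reproduce. The calculation below is an illustration under stated assumptions.

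**Inputs**
- Median OS 21.1 months (section 7.2.3, overall population of Study 017001).
- Registration up to 6 months after infusion (section 9.7.3).
- Assumed, not in the protocol: OS is exponential; a share f of patients registers late, uniformly over months 0 to 6 and independently of prognosis; every death before registration in that share is lost (worst case); all other patients are complete from infusion.

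**True survival**
- Hazard: λ = ln 2 / 21.1 = 0.03285 per month.
- S(3) = 0.9061, S(6) = 0.8211, S(12) = 0.6742. So 9.4% die by month 3 and 17.9% by month 6.

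**Share retained**
- Mean survival to registration among late registrants: (1 − S(6)) / (6λ) = 0.1789 / 0.1971 = 0.9076.
- Share of all infused patients retained: D = (1 − f) + 0.9076 f.
- Survival from infusion as seen in the retained cohort, at month 6 or later: S(t) / D.

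| f | Cohort missing, 1 − D | 6-month OS, 0.8211 / D | 12-month OS, 0.6742 / D |
|---|---|---|---|
| 0 (truth) | 0% | 82.1% | 67.4% |
| 10% | 0.9% | 82.9% | 68.05% |
| 25% | 2.3% | 84.1% | 69.0% |
| 50% | 4.6% | 86.1% | 70.7% |
| 100% | 9.2% | 90.5% | 74.3% |

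The 12-month overstatement is therefore about 0.6, 1.6, 3.3 or 6.9 percentage points.

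**Sensitivity to the survival shape.** With a 40% plateau and the same median, S(t) = 0.4 + 0.6 exp(−kt), where k = ln 6 / 21.1 = 0.0849. True 12-month OS is 61.7%, and the mean of S over months 0 to 6 is 0.8701. Then f = 50% gives 0.6166 / 0.9351 = 65.9%, and f = 100% gives 0.6166 / 0.8701 = 70.9%.

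**Does delayed entry help?** In a simulation of the exponential case, Kaplan-Meier with entry at registration returned about 82% at 6 months and 67% at 12 months for every f above. That rests on registration being independent of prognosis.

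**Toxicity.** Take a true rate of 10.0% for Grade 3 or higher neurotoxicity (27/269, Table 4). If a share a of affected and b of unaffected patients is never entered, the observed rate is 0.10(1 − a) / [0.10(1 − a) + 0.90(1 − b)]. With b = 5%, a = 10%, 20% or 50% gives 9.5%, 8.6% or 5.5%. These loss shares are assumptions; the protocol gives none.

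**The case against.** The strongest reply is that the protocol describes a data-entry window, not a survival condition. Registration may precede infusion, baseline data are entered retrospectively, a legal representative may consent when applicable, and deaths are reported on an event-driven form. Nothing bars entering a patient who died before registration. All of that stands. A reader might infer that such deaths are in fact lost; the documents support only that they may be.

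A second tempting inference is that severe toxicities before registration are lost in general. They are not. Section 9.7.5.2 has CRS, neurotoxicity and the other toxicities except secondary malignancies reported by look-back over the preceding period, so a patient registered late still brings events from the first weeks. Only events in patients never entered are at risk. The source trial reported no fatal CRS or neurotoxicity among 269 patients (section 7.2.3), and several primary endpoints, such as secondary malignancies, are not early events.

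Third, section 9.7.5.1 leaves the time periods and methods for incidences to the SAP, which is not at hand, and the SAP could add delayed entry, since an infusion origin does not exclude it. That is fair as to the estimator. It does not settle the matter: consent timing, the registration window and the analysis sets are fixed in the protocol, and no later analysis recovers patients who were never entered.

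Finally, the reconciliation of shipped product in section 9.9 could reveal infused but unregistered patients. It could, but the protocol presents it as monitoring of reporting and gives it no use in the analysis.

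**Conclusion.** The point holds as a risk that the protocol neither names nor measures. Consent after treatment, registration up to 6 months after infusion, and Kaplan-Meier from infusion with no entry time together can bias early OS and PFS upward, and could understate fatal or incapacitating early toxicity.

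Its size cannot be determined from the documents. The illustrated overstatement of 12-month OS runs from about 0.6 points (10% registered late) to 6.9 points (all registered late). These are upper figures for each share, because they assume that every pre-registration death is lost. If deceased patients are entered retrospectively, the bias shrinks or disappears. The effect on toxicity incidence rests entirely on assumed loss shares. This calls for a sensitivity analysis and clearer reporting, and does not show that the planned estimates are wrong.

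**What to change.** In section 9.7, keep the infusion-origin analysis and add the following.

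1. A prespecified sensitivity analysis of OS with delayed entry at the Patient Registering Date, and likewise of PFS and TTNT with patients whose event precedes registration excluded from the risk set. State that it assumes registration timing is independent of prognosis and that it does not restore lost toxicities.
2. CRS, neurotoxicity and early deaths reported separately for patients registered on or before infusion and those registered after it. Present both, with no rule that one estimate replaces the other.
3. A table of the infusion-to-registration lag by registry, and the infused-but-unregistered count from the reconciliation already planned in section 9.9.

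In section 9.9, name the possible loss of patients who die or become incapacitated before consent or registration.

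The infusion and registering dates are already in Table 3, so no new variable is needed. The cost is a little more analysis and wider intervals early in follow-up, where delayed entry thins the risk set.

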## 9.7.4 Effectiveness Analysis

### 9.7.4.1 Analysis of the Secondary Effectiveness Endpoints

- **Overall response rate (ORR):** ORR is the proportion of patients with a best overall response of complete response (CR) or partial response (PR), where best overall response is defined as the best disease response recorded from liso-cel infusion until disease relapse or progression or start of new anti-cancer therapy, whichever happens first. If best response is collected by both computerized tomography (CT) and positron emission tomography (PET) methods, best response per PET overrules best response per CT.
- **Complete response rate (CRR):** CRR is the proportion of patients with a best overall response of CR, where best overall response is defined as the best disease response recorded from liso-cel infusion until disease relapse or progression or start of new anti-cancer therapy, whichever happens first. If best response is collected by both CT and PET methods, best response per PET overrules best response per CT.
- **Duration of response (DoR):** DoR is defined as the time from the date of first documented disease response (CR or PR) to the date of first documented progression or first documented relapse, or to date of death due to primary disease, whichever happens first. Patients who are alive and didn't experience disease progression, relapse or death due to primary disease before last contact date will be censored at that time, but no censoring will be done for additional treatment.
- **Progression-free survival (PFS):** PFS is defined as the time from the date of first liso-cel infusion to the date of event defined as the first documented relapse or progression or death due to any cause, whatever happens first. Patients who did not reach such events before the last contact date will be censored at that time, but no censoring will be done for additional treatment.
- **Overall survival (OS):** OS is defined as the time from the date of first infusion to the date of death due to any cause. All patients will be followed for survival information, regardless of whether they receive additional treatment postinfusion. Patients who are alive at last contact date will be censored at that time, but no censoring will be done for additional treatment. OS will be calculated according to the formula:  
$$\text{OS (months)} = (\text{date of death or censoring} - \text{infusion date} + 1) / 30.4375.$$
- **Time to next treatment (TTNT):** TTNT is defined as the time from the date of liso-cel infusion to next treatment of the primary disease (excluding consolidation and maintenance therapies). Patients who did not receive any new treatment for the primary disease before the last contact date or before death will be censored at the last contact date or death date. TTNT will be calculated according to the formula:  
$$\text{TTNT (days)} = \text{date of start of the next therapy line or censoring} - \text{infusion date} + 1$$
- **Time-to-Event (TTE) Analysis:** For DoR, PFS, OS, and TTNT, Kaplan-Meier (KM) estimates and the associated 95% CIs of the median, 25th and 75th percentile will be presented. The 2-sided 95% CIs will be computed using the log-log transformation. The survivor function will be displayed graphically using a KM curve.

